10.3.2. Study Phases for AE Data

Assessments and events will be classified according to time of occurrence relative to the start and/or stop date of the study treatment.

Study Phase	Definition
Pre-Treatment	Event Start Date < Initial Study Treatment Date
On-Treatment	If event onset date is on or after the initial treatment date & on or before the final treatment date with 3 days lag time. Initial Study Treatment Date ≤ Event Start Date ≤ Final Study Treatment Date + 3 days
Post-Treatment	If event onset date is after the final treatment date with 3 days lag time. Event Start Date > Final Study Treatment Date + 3 days
Onset Time Since 1 st Dose (Days)	If Treatment Date > Event Onset Date = Event Onset Date – Treatment Date If Treatment Date ≤ Event Onset Date = Event Onset Date – Treatment Date+1 Missing otherwise.
Duration (Days)	Event Resolution Date – Event Onset Date + 1
Drug-related	If relationship is marked 'YES' on eCRF OR value is missing.

NOTES:

- If the initial and final study treatment dates are missing then the event will be considered to be On-Treatment.

10.4. Appendix 4: Data Display Standards & Handling Conventions

10.4.1. Reporting Process

Software	

 The currently supported versions of SAS software will be used. 	
Reporting Area	
HARP Server	: US1SALX00259-HARP PROD-US
HARP Compound	: GSK3365791
Analysis Datasets	

Analysis datasets will be created according to Clinical Data Interchange Standards Consortium (CDISC) standards (SDTM IG Version 3.2 & Analysis Data Model (ADaM) Implementation Guide (ADaM IG) Version 1.0 or higher dataset standards)
	
Generation of RTF Files	

 RTF files will be generated for summary displays. 	

10.4.2. Reporting Standards

General

 The current GSK Integrated Data Standards Library (IDSL) will be applied for reporting, unless otherwise stated (IDSL Standards Location: https://spope.gsk.com/sites/IDSLLibrary/SitePages/Home.aspx): 
 4.03 to 4.23: General Principles 5.01 to 5.08: Principles Related to Data Listings 6.01 to 6.11: Principles Related to Summary Tables 7.01 to 7.13: Principles Related to Graphics
Formats

 GSK IDSL Statistical Principles (5.03 & 6.06.3) for decimal places (DP's) will be adopted for reporting of data based on the raw data collected, unless otherwise stated. Numeric data will be reported at the precision collected on the eCRF. The reported precision from non eCRF sources will follow the IDSL statistical principles but may be adjusted to a clinically interpretable number of DP's.
Planned and Actual Time

 Reporting for tables, figures and formal statistical analyses: 
 Planned time relative to dosing will be used in figures, summaries, statistical analyses and calculation of any derived parameters, unless otherwise stated. The impact of any major deviation from the planned assessment times and/or scheduled visit days on the analyses and interpretation of the results will be assessed as appropriate. Reporting for Data Listings: 
 Planned and actual time relative to study drug dosing will be shown in listings (Refer to IDSL Statistical Principle 5.05.1). Unscheduled or unplanned readings will be presented within the subject's listings.
Unscheduled Visits

 Unscheduled visits will not be included in summary tables and/or figures. All unscheduled visits will be included in listings.

Descriptive Summary Statistics	
Continuous Data	Refer to IDSL Statistical Principle 6.06.1
Categorical Data	N, n, frequency, %
Graphical Displays	

 Refer to IDSL Statistical Principles 7.01 to 7.13. 	

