1.2. Schedule of Activities (SoA)

Table 1 Screening Visit

Procedure	Screening (up to 28 days before Day 1)
Informed Consent	X
Inclusion and exclusion criteria	X
Demographics	X
Brief physical examination including height, weight and body mass index (BMI) ¹	X
Medical history including substance (Drug, Alcohol, Tobacco and Caffeine) usage	X
Urine drug / serum alcohol / Cotinine screening	X
Triplicate 12-Lead Electrocardiogram (ECG) ⁴	X
Vital Sign (VS) measurements ⁴	X
Serum or urine pregnancy test (WOCBP only)	X
Follicle-stimulating hormone (as needed, to confirm postmenopausal status)	X
HIV, Hep B and Hep C Screening ²	X
Clinical laboratory assessments (hematology, chemistry, urinalysis, including liver chemistries) ^{3,4}	X

¹ A brief physical examination will include at a minimum, assessments of the skin, cardiovascular, and respiratory.

² If test otherwise performed within 3 months prior to first dose of study intervention, testing at screening is not required

³ Glucose non-fasting at screening.

⁴ VS, Clinical laboratory assessments, ECG can be repeated once.

Table 2 Study Intervention Period Assessments

Procedure	Day -1	Study Intervention Period										Follow-Up (12-17 days post last dose) 2,3	Notes		
		Day													
		1			2	3	4	6	8	10	12				
		Pre Dose	0 hr	Post Dose	24 hr	48 hr	~72 hr	~120 hr	~168 hr	~216 hr	~264 hr				
Admission to Unit	X														
Discharge						X									
Outpatient Visit							X	X	X	X	X				
Brief Physical Exam ¹	X														
Pregnancy test (urine or serum)	X											X			
Urine/Drug/Alcohol/Cotinine	X												Illicit Drug/Alcohol/Cotinine performed at the standard practice of the site.		
12-Lead ECG	X												Single ECGs will be collected		
Vital Signs (VS) measurements	X	X										X	Single VS measurements will be performed at all time points.		
Safety lab assessments (Hematology,Chemistry)	X					X							Glucose fasting is required approximately 10 hours prior to dosing on Day -1 and at least 6 hours at Day 3 post dose.		
DTG/RPV FDC Dosing			X										1. Subjects will fast for ~10 hours and receive the dose ~30 minutes (\pm 5 minutes) after the start of a standardized moderate fat breakfast		

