Pharmacokinetic Sampling		X		Collected at 0.5, 1, 1.5, 2, 2.5, 3, 3.5, 4, 5, 6, 7, 8, 9, 12, 16, 24, and 48 hours post-dose			X	X	X	X	X		1. Subjects should be scheduled to provide PK samples in the morning on Days 4, 6, 8, 10, and 12; Days 8, 10, and 12 are for RPV sampling only. 2. The 4-hour post-dose sample must be drawn prior to the subjects' first post-dose meal		

Procedure	Day -1	Study Intervention Period										Follow-Up (12-17 days post last dose) 2,3	Notes		
		Day													
		1			2	3	4	6	8	10	12				
		Pre Dose	0 hr	Post Dose	24 hr	48 hr	~72 hr	~120 hr	~168 hr	~216 hr	~264 hr				
Serious Adverse Event (SAE) Review	X	<=====X=====>										X			
Adverse Event (AE) Review		<=====X=====>										X			
Concomitant medication review	X	<=====X=====>										X			

¹ Brief examinations may be made full examinations and laboratory procedures may be repeated, if needed, at the discretion of the investigator.

² If withdrawal is after Day 3, but before Follow Up procedure, please perform all Follow Up study procedures.

³ Follow up study procedures can be performed on Day 12.

- The timing and number of planned study assessments, including safety and PK assessments may be altered during the course of the study based on newly available data (e.g., to obtain data closer to the time of peak plasma concentrations) to ensure appropriate monitoring.
- Any changes in the timing or addition of time points for any planned study assessments as the result of emerging pharmacokinetic data from this study must be documented and approved by the relevant study team member and then archived in the sponsor and site study files, but will not constitute a protocol amendment. The Competent Authority (CA) and ethics committee (EC) will be informed of any safety issues that constitute a substantial amendment and require alteration of the safety monitoring scheme or amendment of the informed consent form (ICF). The changes will be approved by the CA and the EC before implementation.

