9.4. Statistical Analyses

Final analyses will be performed after the completion of the study and final dataset authorization.

Data will be listed and summarized according to GlaxoSmithKline reporting standards where applicable.

Unless stated otherwise, descriptive summaries for continuous variables will include n, mean, standard deviation (SD), median, minimum, maximum; whereas, n and percent will be used as summary statistics for categorical variable. Geometric mean with

associated 95% CI, and the between-subject coefficient of variance (CV) (%CVb) for the geometric mean will be included for PK variables, where applicable.

Baseline or pre-dose assessment is the last available assessment prior to time of the first dose unless it is specified otherwise. If there are multiple assessments collected on the same scheduled time, the average of these assessments will be used. For tabulated safety summaries, only the scheduled assessments will be included in the summary tables.

Version 9.4 or higher of the Statistical Analysis Software (SAS) system will be used to analyze data as well as to generate tables, listings, and figures.

Complete details will be documented in the Reporting and Analysis Plan (RAP).

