10.9.4. Safety Tables

Safety: Tables					
No.	Population	IDSL / Example Shell	Title	Programming Notes	Deliverable [Priority]
Adverse Events (AEs)					
3.1.	Safety	AE1	Summary of All Adverse Events by System Organ Class and Preferred Term		SAC [1]
3.2.	Safety	AE1	Summary All Drug-Related Adverse Events		SAC [1]
3.3.	Safety	AE5a	Summary of Adverse Events by Maximum Grade by System Organ Class and Preferred Term		SAC [1]
Laboratory: Chemistry					
3.4.	Safety	LB1	Summary of Chemistry Values		SAC [1]
3.5.	Safety	LB1	Summary of Chemistry Changes from Baseline	Add Footnote - Note: Baseline is defined as Day -1	SAC [1]
3.6.	Safety	LB16	Summary of Chemistry Results by Maximum Grade Increase Post-Baseline Relative to Baseline		SAC [1]
Laboratory: Hematology					
3.7.	Safety	LB1	Summary of Hematology Values		SAC [1]
3.8.	Safety	LB1	Summary of Hematology Changes from Baseline	Add Footnote - Note: Baseline is defined as Day -1	SAC [1]
3.9.	Safety	LB16	Summary of Hematology Results by Maximum Grade Increase Post-Baseline Relative to Baseline		SAC [1]

Safety: Tables					
No.	Population	IDSL / Example Shell	Title	Programming Notes	Deliverable [Priority]
Laboratory: Urinalysis					
3.10.	Safety	LB1	Summary of Urinalysis Dipstick Results		SAC [1]
Laboratory: ECG					
3.11.	Safety	EG1	Summary of ECG Findings		SAC [1]
Vital Signs					
3.12.	Safety	VS1	Summary of Vital Signs		SAC [1]
3.13.	Safety	VS1	Summary of Change from Baseline in Vital Signs	Add Footnote - Note: Baseline is defined as Day 1 (Predose)	SAC [1]

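### Tables 3.6 and 3.9 are titled as maximum post-baseline laboratory grades but, under the rules as written, report the Day 3 grade only (minor, cheap to improve)

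*SAP*

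**What the plan says.** **Tables.** SAP 10.9.4 plans Table 3.6, "Summary of Chemistry Results by Maximum Grade Increase Post-Baseline Relative to Baseline", and Table 3.9, "Summary of Hematology Results by Maximum Grade Increase Post-Baseline Relative to Baseline". Both use the Safety population and shell LB16, and their programming notes are empty.

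**Rule.** Protocol 9.4 states: "For tabulated safety summaries, only the scheduled assessments will be included in the summary tables". SAP 10.4.2 states: "Unscheduled visits will not be included in summary tables and/or figures". The same SAP section sends the excluded data to the listings: "Unscheduled or unplanned readings will be presented within" each participant's listings. It also says that the sponsor's display standards (IDSL) "will be applied for reporting, unless otherwise stated".

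**Schedule.** In Protocol 1.2, Table 2, the row "Safety lab assessments (Hematology,Chemistry)" is marked at Day -1 and Day 3 (48 h). SAP 10.2.1 repeats the row. SAP 5.2 makes Day -1 the laboratory baseline.

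**Off-schedule samples.**
- Protocol 8 permits repeat or unscheduled samples for safety or technical reasons.
- Protocol 8.2.4 calls for clinically significant abnormal values, arising during participation or up to 17 days after dosing, to be repeated until they normalise, return to baseline or are no longer significant.
- Appendix 6 requires repeat liver chemistries within 24 hours or within 24-72 hours, depending on the pattern. Monitoring then runs twice weekly or weekly until the values resolve, stabilise or return to baseline.

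**The concern.** Leaving irregular draws out of a by-visit mean is sensible, because they would blur the visit. A worst-value table has a different purpose: a maximum over the post-baseline period should include the later samples, and samples taken because something looked abnormal are the ones most likely to carry a worse grade.

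Two situations are affected:

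- A Day 3 abnormality that worsens on repeat is tabulated at its lower Day 3 grade.
- A graded abnormality first found on an off-schedule sample is not tabulated at all.

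In both, the table shows a lower worst grade than the laboratory listings do, under a title that promises the maximum. These are the only two planned tables of worst post-dose laboratory grade.

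**Working it through.** No figure in the plan needs reproducing. The check is a count, followed by a reading of the rules together.

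**1. Scheduled draws.** The chemistry and haematology row is marked at Day -1 and Day 3 in both documents. The fasting-glucose note in that row names the same two days, so the reading does not depend on how the table columns were extracted. The follow-up column has vital signs and a pregnancy test but no safety laboratory tests. Follow-up may also be brought forward ("Follow up study procedures can be performed on Day 12"), which adds no draw. Scheduled draws: 2. Baseline draws: 1. Scheduled post-baseline draws: 2 - 1 = 1.

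**2. Effect of the rule.** If only scheduled results are eligible, the maximum for each analyte and participant is taken over one value, so max{Day 3 grade} = Day 3 grade.

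**3. Ways the text might escape this.**

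| Possible escape | Outcome |
|---|---|
| SAP 10.4.2 speaks of unscheduled visits, so an extra draw at a scheduled outpatient visit (Day 4, say) might count | Protocol 9.4 speaks of assessments, which closes this gap |
| A repeat assigned to the Day 3 time point might be included | SAP 10.5.1 averages multiple measurements at one time point, which would dilute a worse grade |
| Protocol 8.2 allows safety time points to be added | True; the point is limited to the schedule as written |
| Shell LB16 might include unscheduled results | The shell is not in the documents; IDSL yields where the SAP states otherwise, and SAP 10.4.2 does state a rule |

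**4. Where else such a result would appear.**

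- Protocol 8.2.4 has clinically relevant laboratory changes recorded as AEs, and Appendix 3 includes clinically significant abnormal results in the AE definition. These reach Table 3.1, and Table 3.3 by maximum grade.
- Liver events have their own CRF and Listing 29.
- Laboratory abnormalities are shown in Listings 18-21.
- The remainder is a graded off-schedule result, worse than Day 3, that is not recorded as an AE. It appears in a listing but in no table.

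**5. Size.** Affected displays: 2 of the 13 safety tables (3.1 to 3.13). The documents do not say how many off-schedule results to expect, so no expected understatement can be calculated. For scale only: if all 16 participants (the enrolment maximum) are dosed and one participant's only grade increase is off-schedule, the table shows 0/16 = 0% instead of 1/16 = 6.3%. With 13 dosed, the missing entry would be 1/13 = 7.7%. The 13 is the target for evaluable completers, used here only to give a range.

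**The case against.** The strongest reply is that this is a deliberate rule, stated in the protocol and carried consistently into the SAP. That stands: there is no contradiction between the documents. A reader might infer that safety data are lost or concealed. The documents do not support this, because the SAP expressly sends unscheduled results to the listings, and with at most 16 participants those can be read directly.

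Second, the gap is narrow. The repeats in Protocol 8.2.4 follow from clinically significant values, which should already be AEs, and liver events are followed and listed separately. This also stands, and it is the main reason for calling the point minor. It does not close the gap, because AE recording depends on the investigator's judgement and a result can be graded without being judged clinically relevant.

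Third, the study has one arm, safety is a secondary objective, and no hypothesis is tested. No decision rule or primary endpoint uses Tables 3.6 or 3.9. That is correct.

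Fourth, shell LB16 was not available, and a sponsor might treat the Appendix 6 repeats as planned. Protocol 9.4 makes the exclusion the more natural reading, though not a certain one. If the sponsor means to include those samples, the SAP still needs a sentence saying so.

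A reader might also take the share of follow-up after Day 3 as the size of the problem: (264 - 48)/264 = 82% if follow-up is done on Day 12, or (17 - 2)/17 = 88% if it is done at 17 days. That share describes the sampling schedule. No laboratory draws are scheduled in that window, so it says nothing about how many results the table rule excludes.

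**Conclusion.** The point holds as a minor, cheap improvement. As written, Tables 3.6 and 3.9 give the Day 3 grade, and a worse grade on a valid off-schedule sample would not be tabulated. The pharmacokinetic analysis and the by-visit summaries are untouched.

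The effect is zero if no off-schedule result is worse than Day 3. Otherwise it is largely offset by the AE tables and the listings. What is left is an unknown, possibly nil, number of graded results not recorded as AEs, together with a title that claims more than one time point can give.

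The conclusion assumes that no laboratory time point is formally added under Protocol 8.2, that the written rule prevails over shell LB16, and that repeats under Protocol 8.2.4 and Appendix 6 count as unscheduled.

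**What to change.** Preferred change:

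- **SAP 10.4.2:** keep the exclusion for by-visit summaries (Tables 3.4, 3.5, 3.7 and 3.8). For Tables 3.6 and 3.9, use all valid post-dose results in the final database, scheduled or unscheduled, including repeats under Protocol 8.2.4 and Appendix 6 taken after the follow-up visit. A cut-off at the end of follow-up would be too early: the 17 days in Protocol 8.2.4 limit when the abnormal value arises, not when repeats stop. Exclude results invalidated for technical reasons. Leave the SAP 5.2 baseline as it is.
- **SAP 10.5.1:** add a matching exception so that post-baseline results are graded individually, not averaged, for these two tables. Without it the two sections would conflict.
- **SAP 2.1:** declare the change from Protocol 9.4, since this section now reports none.
- **Tables 3.6 and 3.9:** footnote which results are included.

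The cost is a declared departure from Protocol 9.4, a few sentences, one programming filter and two footnotes. No new data are needed.

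If the sponsor keeps the Protocol 9.4 rule, the minimum is a footnote on both tables: *Scheduled Day 3 draw only; see Listings 18-21 for unscheduled results.* That corrects the label but leaves the possible understatement.

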10.4.3. Reporting Standards for Pharmacokinetic

Pharmacokinetic Concentration Data	
PC Windows Non-Linear (WNL) File	PC WNL file (CSV format) for the non-compartmental analysis by Clinical Pharmacology Modelling and Simulation function will be created according to [Insert document name]. Note: Concentration values will be imputed as per GUI_51487
Descriptive Summary Statistics, Graphical Displays and Listings	Refer to IDSL PK Display Standards. Refer to IDSL Statistical Principle 6.06.1. Note: Concentration values will be imputed as per GUI_51487 for descriptive summary statistics/analysis and summarized graphical displays only.
Pharmacokinetic Parameter Derivation	
PK Parameter to be Derived by CPMS	The following PK parameters will be derived by the CPMS: Plasma DTG and RPV AUC _(0-∞) , AUC _(0-t) , C _{max} , t _{lag} , t _{max} , t, t _{1/2} , λ _z , %AUC _{ex} , AUC ₍₀₋₂₄₎ , AUC ₍₀₋₇₂₎ , CL/F and Vz/F, C _t , and C ₂₄
Pharmacokinetic Parameter Data	
Is NQ impacted PK Parameters Rule Being Followed	Refer to [Standards for Handling NQ Impacted PK Parameters].
Descriptive Summary Statistics, Graphical Displays and Listings	Refer to IDSL PK Display Standards. Refer to IDSL Statistical Principle 6.06.1.

10.5. Appendix 5: Derived and Transformed Data

10.5.1. General

Multiple Measurements at One Analysis Time Point

 Mean of the measurements will be calculated and used in any derivation of summary statistics but if listed, all data will be presented. Participants having both High and Low values for Normal Ranges at any post-baseline visit for safety parameters will be counted in both the High and Low categories of “Any visit post-baseline” row of related summary tables. This will also be applicable to relevant Potential Clinical Importance summary tables.
Study Day

 Calculated as the number of days from First Dose Date: 
 Ref Date = Missing → Study Day = Missing Ref Date < First Dose Date → Study Day = Ref Date – First Dose Date Ref Date ≥ First Dose Date → Study Day = Ref Date – (First Dose Date) + 1

10.5.2. Study Population

Age

 GSK standard IDSL algorithms will be used for calculating age where birth date will be imputed as follows: 
 Only the year of birth will be collected. The date and month will be imputed as ‘30th June’. Birth date will be presented in listings as ‘YYYY’.
Body Mass Index (BMI)

 Calculated as Weight (kg) / [Height (m)²]

10.5.3. Safety

Adverse Events
AE'S of Special Interest

 No analysis for AEs of Special Interest will be performed.

ECG Parameters
RR Interval

 IF RR interval (msec) is not provided directly, then RR can be derived as: 
 If QTcB is machine read & QTcF is not provided, then: $RR = \left[\left(\frac{QT}{QTcB} \right)^2 \right] * 1000$ If QTcF is machine read and QTcB is not provided, then: $RR = \left[\left(\frac{QT}{QTcF} \right)^3 \right] * 1000$ If ECGs are manually read, the RR value preceding the measurement QT interval should be a

ECG Parameters
collected value THEN do not derive.

Machine read values of RR should not be replaced with derived values.
Corrected QT Intervals

When not entered directly in the eCRF, corrected QT intervals by Bazett's (QTcB) and Fredericia's (QTcF) formulas will be calculated, in msec, depending on the availability of other measurements.IF RR interval (msec) is provided then missing QTcB and/or QTcF will be derived as:
$QTcB = \frac{QT}{\sqrt{\frac{RR}{1000}}}$
$QTcF = \frac{QT}{\sqrt[3]{\frac{RR}{1000}}}$

10.6. Appendix 6: Reporting Standards for Missing Data

10.6.1. Premature Withdrawals

Element	Reporting Detail
General	
 Subject study completion (i.e. as specified in the protocol) was defined as if he/she has completed all phases of the study including the last visit or the last scheduled procedure as shown in the Schedule of Activities. Withdrawn subjects were not replaced in the study. All available data from participants who were withdrawn from the study will be listed and all available planned data will be included in summary tables and figures, unless otherwise specified.

10.6.2. Handling of Missing Data

Element	Reporting Detail
General	
 Missing data occurs when any requested data is not provided, leading to blank fields on the collection instrument: 
 These data will be indicated by the use of a “blank” in subject listing displays. Unless all data for a specific visit are missing in which case the data is excluded from the table. Answers such as “Not applicable” and “Not evaluable” are not considered to be missing data and should be displayed as such.
Outliers	
 Any participants excluded from the summaries and/or statistical analyses will be documented along with the reason for exclusion in the clinical study report.

